11.1 VFQ-25 Questionnaire

Subjects will complete the VFQ-25 at the times indicated in Table 3. The VFQ-25 must be completed by the subject at the beginning of the study visit, before any significant interaction with the study staff.

This questionnaire measures dimensions of self-reported vision-targeted health status that are most important to persons with eye disease (Mangione 2001). Improvement in the VFQ-25 will be evaluated using individual scores, subscale scores, and the overall composite score. The VFQ-25 will only be conducted in languages in which a validated translation is available.

11.3 Best Corrected Visual Acuity

To evaluate changes in VA over the study period, BCVA will be assessed for both eyes using the ETDRS VA chart at the times indicated in Table 3.

The BCVA test should be performed prior to pupil dilation, and distance refraction should be carried out before BCVA is measured. Initially, letters are read at a distance of 4 metres from the chart. If <20 letters are read at 4 metres, testing at 1 metre should be performed. BCVA is to be reported as number of letters read correctly by the subject. At the Screening/Baseline Visit, eyes with a BCVA of 34-73 ETDRS letters (equivalent to worse than or equal to 6/12 or 20/40 Snellen acuity, but better than or equal to 6/60 or 20/200 Snellen acuity) will be eligible for the study.

If a subject cannot read any letters on the BCVA chart, the subject will be tested for finger counting, hand movements or light perception. Refer to the Site Operations manual for full details.

11.4 Contrast Sensitivity

Contrast sensitivity will be measured for both eyes at the times indicated in Table 3.

Contrast sensitivity will be measured prior to pupil dilation using a Pelli-Robson chart.

11.5 Colour Vision

Colour vision will be tested for both eyes prior to pupil dilation at the times indicated in Table 3.

Eyes will be tested separately and in the same order at each assessment. Refer to the Study Operations Manual for details on the colour vision test to be used.

11.6 Reading Speed Test

Reading performance will be evaluated prior to pupil dilation at the times indicated in Table 3 using International Reading Speed Texts (IReST), which provide standardised assessment of reading performance in 17 languages (Trauzettel-Klosinski 2012). The IReST will be provided to each site by the Sponsor, and for complete user instructions refer to the Study Operations Manual (which will include the randomisation procedure for text selection). The IReST will only be conducted in languages in which a validated translation is available.

11.7 Microperimetry

Microperimetry will be conducted for both eyes at the times indicated in Table 3.

Microperimetry will be conducted by certified technicians to assess changes in retinal sensitivity within the macula. All microperimetry images will be sent by the sites to a Central Reading Centre (CRC) for review. For complete technical specifications for microperimetry, refer to the Study Operations Manual (which will include procedures from the CRC regarding how measurements are to be taken).

11.8 Fundus Autofluorescence

To assess changes in the area of viable retinal tissue, fundus AF will be performed for both eyes at the times indicated in Table 3.

All fundus AF images will be performed by certified technicians at the site after dilation of the subject's pupil and sent to a CRC for review. For complete technical specifications for fundus AF, refer to the Study Operations Manual (which will include procedures from the CRC regarding how measurements are to be taken).

11.9 Spectral Domain Optical Coherence Tomography (SD-OCT)

SD-OCT will be performed for both eyes at the times indicated in Table 3.

SD-OCT measurements will be taken by certified technicians at the site after dilation of the subject's pupil. All OCT scans will be submitted by the sites to a CRC where the scans will be evaluated. SD-OCT will be used to assess a number of variables, including quantifying the integrity of the ellipsoid zone and reduction in the signal from the outer nuclear layer and choroid. In addition, since progressive foveal thickening has been noted in the early phase of CHM (Jacobson 2006), foveal changes will be assessed. For complete technical specifications for SD-OCT, refer to the Study Operations Manual (which will include procedures from the CRC regarding how measurements are to be taken).

12 ASSESSMENT OF SAFETY

12.1 Full Ophthalmic Examination

A full ophthalmic examination will be conducted for both eyes at the times indicated in Table 3.

For subjects in the AAV2-REP1 groups, the full ophthalmic examination will be conducted prior to pupil dilation and prior to vitrectomy and administration of study medication at the applicable study visit.

The ophthalmic examination will include IOP, slit lamp examination, lens opacity grading, and dilated ophthalmoscopy. The same slit lamp machine and lighting conditions should be used across study visits for any given subject.

In addition to the parameters listed above, relevant subjects will be carefully examined for the presence of intraocular inflammation after vector administration. Cataract can also develop as a result of the vitrectomy procedure and can potentially affect VA. Pre-operative grading of lens opacity and colour should therefore be documented by the established clinical lens opacities classification system. A recent study has shown that cataract surgery is effective in subjects with CHM and without any specific risks (Edwards 2015). Hence, if clinically indicated, subjects who develop cataracts may undergo cataract surgery. If cataract surgery is performed, it should be carried out at least 4 weeks before the Month 12 Visit/EOS Visit.

12.2 7-Field Colour Fundus Photography

To aid in the objective clinical assessment of progressive retinal changes, 7-field colour fundus photography will be performed for both eyes at the times indicated in Table 3.

Fundus photography will be performed by certified technicians following pupil dilation. Stereo photos should be performed for fields 1, 2, and 3. All fundus photographs will be sent by the sites to the CRC for review. For complete technical specifications for fundus photography, refer to the Study Operations Manual (which will include procedures from the CRC regarding how measurements are to be taken).

12.3 Evaluation, Recording, and Reporting Adverse Events

12.3.1 Definitions

12.3.1.1 Adverse Event

An AE is any untoward medical occurrence in a clinical investigation subject, which does not necessarily have a causal relationship with the study medication/surgical procedure. An AE can therefore be any unfavourable and unintended sign (including an abnormal laboratory finding), symptom, or disease temporally associated with the use of the study medication / surgical procedure, whether or not related to the investigational product or with the surgical procedure described in this protocol.

AEs are to also include any pre-existing condition (other than CHM) or illness which worsens during the study (i.e., increases in frequency or intensity).

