Loss of visual acuity (VA) has been observed post-treatment with AAV2-REP1. This VA loss was determined by investigators to be plausibly related to the administration of AAV2-REP1, however without definitively attributing the cause to either the study procedure or the GTMP. Loss of VA is, therefore, considered a Potential Risk of AAV2-REP1 treatment, in addition to the above-described potential and anticipated surgical risks. See the Investigator's Brochure for AAV2-REP1 for further details.

Thus, although there are risks associated with the administration of the study treatment via vitrectomy and retinal detachment, the potential for benefit in the form of improved VA potentially provided to subjects with CHM following treatment with AAV2-REP1 provides an acceptable benefit-risk profile for participation in this study.

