These treated subjects will then return to the site for 2 post-operative follow up visits on Day 1 (Visit 3) and, possibly, Day 7 (Visit 4; Day 7 can occur either at the surgical site or the host site, depending on the clinical status of the subject). Subjects in the Control group will not undergo surgery, receive study drug or attend the 2 on-site safety post-operative visits.

Instead, a telephone contact from the site will occur for the Control group on Day 0 (Visit 2), Day 1 (Visit 3) and Day 7 (\pm 3 days; Visit 4).

All subjects will be followed for 12 months from Visit 2 (Day 0). Study data will be collected for both eyes of each subject.

Since AAV2-REP1 treatment requires an invasive surgical procedure under general anaesthesia, the sponsor, investigator and the subject will be unmasked to the study procedure (i.e. vitrectomy and sub-retinal injection), however within the treated groups, the sponsor, investigator and subject will be masked to the assigned dose $(1.0 \times 10^{11} \text{ gp or } 1.0 \times 10^{10} \text{ gp})$. To further minimise the potential bias of the treated and untreated eye evaluations, all subjective ophthalmic assessments from the Screening/Baseline period (Visit 1) and from Month 1 (Visit 5) onwards, will be conducted by a masked assessor. Subjects will be assessed for efficacy and safety throughout the study as indicated in the Schedule of Study Procedures (see Section 17.1).

The efficacy evaluation will be based on BCVA, fundus AF, SD-OCT, microperimetry, contrast sensitivity, colour vision, reading speed test, VFQ-25

. The safety evaluation will be based on full ophthalmic examination (including IOP, slit lamp examination, lens opacity grading, and dilated ophthalmoscopy), fundus photography, adverse event (AE) reporting, laboratory assessments (immunogenicity), and vital signs. Any safety information collected as a result of the efficacy assessments (e.g., BCVA) will also be used in the overall safety evaluation, as appropriate.

Subjects who develop cataracts may undergo cataract surgery if deemed clinically necessary; if surgery is performed, it should be carried out at least 4 weeks before the Month 12 Visit/End of Study (EOS) Visit (primary endpoint).

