12.3.1.2 Serious Adverse Event

An SAE is defined as any untoward medical occurrence that:

- Results in death
- Is life-threatening
- Requires inpatient hospitalisation or prolongation of existing hospitalisation
- Results in persistent or significant disability/incapacity
- Is a congenital anomaly/birth defect
- Results in vision loss or is vision threatening
- Is an other important medical event(s).

The term 'life-threatening' in the definition of 'serious' refers to an event in which the subject is at risk of death at the time of the event. It does not refer to an event that hypothetically might cause death if it were more severe.

Hospitalisation for a pre-existing condition, including elective procedures, which has not worsened, does not constitute an SAE.

Other events that may not result in death, are not life threatening or do not require hospitalisation, may be considered an SAE when, based upon appropriate medical judgment, the event may jeopardise the subject and may require medical or surgical intervention to prevent one of the outcomes listed above.

Vision Loss to Be Reported as a Serious Adverse Event

Vision Loss NOT TO BE Reported as an SAE:

• Surgery-related BCVA decrease of ≥15 letters on ETDRS chart occurring within 1 day of surgery, but recovering / resolving at post-operative Days 7 and 14.

Vision Loss or Vision-Threatening Event TO BE Reported as an SAE:

- Surgery-related BCVA decrease of ≥15 letters on ETDRS chart that occurs within 1 day of surgery and that has not recovered* by the 1-Month Visit.
- A decrease in BCVA of ≥15 letters on ETDRS chart that occurs within 1 day of surgery, however, in the investigator's opinion:
 - Has an evolution not consistent with the expected post-operative course;
 - May be attributable to a complication that occurred during surgery, or another untoward event, or the study drug;
 - Actually or potentially requires any surgical or medical intervention to prevent permanent loss of vision.
- Non-surgery-related, sustained (>48 hours duration) decrease from baseline in BCVA of ≥15 letters on ETDRS chart.

*Recovery / Resolution of BCVA loss is defined as a return to baseline BCVA within 5 letters on the ETDRS chart.

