The rationale for including alternative data ascertainment, especially out of window visits in the primary analysis is the following: 1) It is in line with FDA and EMA guidance (U. S. Food and Drug Administration 2020, EMA 2020) on handling analysis during COVID-19 pandemic; 2) No further improvement in the treated patients is expected after the initial response around roughly 1-3 months, if any, post one-time injection of this gene therapy. Therefore, including the out of window visit, especially the visits beyond Month 12 scheduled window for the treated patients is considered a conservative approach considering potential trend of natural disease progression in the long-term follow up; 3) Very slow progression is expected in untreated control patients. The natural history study NIGHT showed an average of 0.5 letters of vision loss in untreated patients during 20 months follow up. Therefore, minimum impact on the analysis is expected from the usage of visits a few months post protocol defined window for the untreated patients, especially for the primary endpoint proportions of >= 15 letters increase from the baseline in BCVA.

Sensitivity analysis will be performed on the primary endpoint and the key secondary endpoints if applicable. The main analyses described in Section 10.1 and Section 10.2 will be repeated as follows:

- On the ITT population excluding subjects who withdraw from the study or died due to COVID-19 without any imputations, but include data collected by alternative ascertainment approaches.
- On the ITT population, where assessments performed at local non-study sites are replaced by the ad-hoc visit assessment (where available), irrespective of the interval between the ad-hoc visit and the local non-study site visit.
- On the ITT population, multiple imputation based on missing at random (MAR) will be applied to impute the data collected by alternative ascertainment approaches with Month 12 visit more than 2 months prior or 3 months after the protocol defined visit window or data missing from early termination or death due to COVID-19. In this

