- Treatment-related (study drug or study procedure) serious TEAEs by SOC and PT
- Study procedure-related serious TEAEs by SOC and PT
- Study drug-related serious TEAEs by SOC and PT
- TEAE leading to death by SOC and PT

In the summary, subjects may be counted under multiple SOCs and PTs, but for each SOC and PT, subjects are only counted once. If a subject experiences the same AE at more than one severity, the most severe rating will be given precedence.

If a subject experiences the same AE at more than one relationship to study drug/procedure, causal relationship will be given precedence over no causal relationship. However, where a causal relationship is identified by the Investigator, the subject will be counted once within each sub-category (related to Study Drug, related to Study Procedure, related to both Study Drug and Study Procedure unknown). In the summary tables, related events are defined as events that are assessed by the investigator to be related to study drug/procedure/both or with an unknown relationship.

Separate additional summaries will be provided for adverse events classified as Ocular Inflammation and Visual Acuity Reduced. The lists of PTs assigned to Ocular Inflammation and Visual Acuity Reduced are provided in a separated document (BIIB111 Signal Detection Plan). The following summaries will be provided by treatment:

- Ocular Inflammation-related TEAEs by SOC and PT
- Ocular Inflammation-related TEAEs by SOC and PT, and by time to onset (≤30 days; >30 days)
- Visual Acuity Reduced-related TEAEs by SOC and PT
- Visual Acuity Reduced-related TEAEs by SOC and PT, and by time to onset (≤30 days; >30 days)

Imputation rules for partial dates are presented in Appendix 3.

Summaries presenting frequency of AEs by SOC and PT will be ordered by descending frequency of SOC in the High Dose group and then, within a SOC, by descending frequency of PT in the High Dose group.

The following listings will be provided:

- All AEs
- AEs reported by subjects who discontinued from the study due to an AE
- All SAEs

• AEs leading to death

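### The CHM exception in the AE definition lets vision losses under 15 letters drop out of the AE data by unmasked attribution, and SAP Section 11 has no table of measured loss to check against

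*Protocol*

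**What the plan says.** Protocol 12.3.1.1 gives two statements. The general definition covers any unfavourable sign, symptom or disease, "whether or not related to the investigational product or with the surgical procedure described in this protocol". The next paragraph adds worsening conditions, with an exception: "AEs are to also include any pre-existing condition (other than CHM) or illness which worsens during the study".

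Protocol 12.3.1.2 counts an event as serious if it "Results in vision loss or is vision threatening". Its list of vision losses to be reported as SAEs includes: "Non-surgery-related, sustained (>48 hours duration) decrease from baseline in BCVA of ≥15 letters on ETDRS chart". Neither line has an exception for CHM.

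Protocol 5.4 states: "Loss of VA is, therefore, considered a Potential Risk of AAV2-REP1 treatment". It gives no letter threshold, and it records that investigators could not firmly assign earlier losses to the procedure or the product.

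Protocol 7.1 says that "the sponsor, investigator and the subject will be unmasked to the study procedure"; masking within the treated arms covers dose only. Under 12.3.2, severity and relationship are assessed at the site by the investigator or a medically qualified designee.

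SAP 11.1 summarises this risk through "Visual Acuity Reduced-related TEAEs by SOC and PT", overall and split at 30 days from onset. SAP 11.8 relates the same AEs to immunogenicity.

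**The concern.** Loss of acuity is both a named risk of treatment and the way CHM itself progresses. If a loss ascribed to CHM need not be entered as an AE, the count of the named risk depends on a judgement of cause by someone who knows whether the eye was operated on.

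That judgement can differ between arms in two ways. Late losses in treated eyes may be put down to CHM, which would hide harm. Losses in control eyes may be put down to CHM more readily than losses in treated eyes, which would inflate the excess. The tables for onset after 30 days are the most exposed, because a surgical cause is then less obvious. What is at stake is the reliability of the dedicated AE summary of a named risk. The primary efficacy analysis is not affected.

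**Working it through.** The plan states no figure on this point, so there is none to reproduce. The check sets the passages side by side and then illustrates the size.

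**1. What happens to a non-surgery-related loss, by size**

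- *At least 15 letters, sustained.* The exception in 12.3.1.1 points to leaving it out if it is called CHM. Section 12.3.1.2 requires an SAE report on measured letters, with no CHM exception. The specific rule is the better reading, so the loss is captured. The protocol does not say which section governs.
- *Under 15 letters.* The general definition in 12.3.1.1 points to recording it; the CHM exception points the other way. The instruction in 12.3.2 to record all AEs whether or not attributed covers attribution to study medication or surgery, not to CHM. No specific rule settles the matter.

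**2. Where measured loss would appear independently of attribution**

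- Key secondary endpoint 3 (SAP 4.2): its complement is a loss of at least 5 letters by arm. It is an ITT efficacy endpoint for Month 12 only, with one cut-off, and missing data count as failure (SAP 10.2).
- SAP 11.8: eyes with a loss of at least 15 letters at Month 12, by treatment group and eye, but only within immunogenicity strata.
- Mean BCVA change at Months 4, 8 and 12 (SAP 10.5): gives no count of eyes that lost vision.
- Protocol 7.1: BCVA will also inform the safety evaluation as appropriate, with no threshold or table.
- The rest of SAP Section 11: no table of measured BCVA loss by arm, eye and visit. The text of the exploratory Section 10.6 is not visible in the public SAP, so this statement is limited to Section 11.

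**3. Expected loss from CHM over the trial**

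SAP 5.5: "The natural history study NIGHT showed an average of 0.5 letters of vision loss in untreated patients during 20 months follow up". Scaled to 12 months: 0.5 × 12/20 = 0.3 letters on average.

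**4. Illustration of size (all rates assumed)**

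The documents give no SD for BCVA change and no rate of loss. Assume a normal 12-month change with mean m from −0.3 to −5 letters and SD s from 5 to 10. With continuity correction, P(loss ≥5) = Φ((−4.5 − m)/s) and P(loss ≥15) = Φ((−14.5 − m)/s).

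- m = −0.3, s = 5: P(loss ≥15) = 0.0023 and P(loss 5–14) = 0.1982. The share of losses of at least 5 letters that are under 15 is 0.1982/0.2005 = 99%.
- m = −5, s = 10: P(loss ≥15) = 0.1711 and P(loss 5–14) = 0.3489. The share is 0.3489/0.5200 = 67%.

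So 67% to 99% of such losses lie below the SAE threshold across this range.

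For an arm of 64, recorded count = 64 × true rate × (1 − fraction ascribed to CHM):

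- 10% true, 75% ascribed: 64 × 0.10 × 0.25 = 1.6 of 6.4.
- 30% true, 25% ascribed: 64 × 0.30 × 0.75 = 14.4 of 19.2.

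Between two arms of 64, high dose and control:

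- *False excess.* True rate 20% in both. With 25% ascribed in the treated arm, 9.6 are recorded (15%); with 75% ascribed in control, 3.2 are recorded (5%).
- *Hidden excess.* True rate 30% treated and 10% control. With 75% ascribed in the treated arm and 25% in control, 4.8 are recorded in each (7.5% v 7.5%).

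**The case against.** The strongest reply has four parts.

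- *The exception only declines to add a category.* The sentence says what AEs also include; it removes nothing from the general definition above it, and the seriousness criterion on vision loss carries no letter threshold. No passage describes a step at which the investigator decides whether a loss is CHM. This stands in part: the undercount is possible, not certain. But if the general definition already covers every loss, the exception has no effect on vision, and the protocol does not tell sites so.
- *Large losses are SAEs anyway.* This stands. A reader might infer that any post-treatment loss called CHM escapes AE reporting; 12.3.1.2 does not allow that for sustained losses of at least 15 letters.
- *Masked assessors measure BCVA in both eyes, and planned summaries by arm and visit show the 5th percentile and minimum.* This stands in part. It means harm need not stay hidden, but none of the planned outputs counts eyes that lost vision by arm, eye and visit in the safety population.
- *The AE table may be built more broadly than it looks.* The preferred terms are listed in a separate signal detection plan that is not available here. That list can select only among events that were entered.

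A reader might also divide a 10-letter loss by the 0.3-letter average and conclude that such a loss cannot be CHM. That compares one eye with a group mean. Without an SD it says nothing about how often individual eyes lose 10 letters.

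**Conclusion.** The point holds for losses under 15 letters. The protocol is ambiguous on whether a smaller loss ascribed to CHM is an AE, the person resolving the ambiguity knows treated from control, and the Visual Acuity Reduced tables count only what was entered. They can undercount, and the comparison between arms can be biased either way. For sustained losses of at least 15 letters there is an unreconciled conflict in wording, but the SAE rule captures them on the better reading.

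The size cannot be derived from the documents. The ranges above rest on assumed rates of loss, spread and attribution, and show only that the effect could matter if attribution differs by arm. The natural-history average suggests that CHM explains little loss over 12 months on average, which weakens the reason for an exception covering vision; it does not identify the cause in any one eye. The documents do not support saying that harm would be concealed, that the tables will undercount, or that bias favours one arm.

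**What to change.** 1. **Protocol.** Reconcile 12.3.1.1 with 12.3.1.2 so that the CHM exception does not let a measured vision loss go unrecorded because of its suspected cause. State explicitly that the vision-loss SAE criteria apply irrespective of attribution to CHM, as their wording already implies. Whether a letter threshold should apply to AE recording, and which, is for the sponsor to set.
2. **SAP Section 11.** Add a descriptive table for the safety population: number and percentage of eyes with measured BCVA loss from baseline of, for example, at least 5, 10 and 15 letters, by arm, eye (study and fellow) and visit (Months 1, 4, 8 and 12), on observed data. These cut-offs serve tabulation only and are not reporting rules.

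The table needs no new data, because BCVA is already scheduled in both eyes at those visits, and it would work even if site recording could no longer be changed. The cost is protocol wording and site guidance, one more table, and somewhat more AE entries, some of which will reflect measurement noise or true progression in control and fellow eyes.
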